## **10.2 Visit 2: Day 2**

1. Record any Adverse Experiences
2. Record times when patient received unfractionated heparin or noncompliance to medication
3. Collect blood for aPTT and anti-Xa 6 hours after second dose of heparin (~15:00 PM on day 2)
4. Follow-up aPTT
  - a. If  $<$  36.2 seconds, continue current dose of heparin
  - b. If  $\geq$  36.2 seconds, adjust heparin dose and repeat aPTT, anti-Xa, and serum creatinine per protocol (APPENDIX 1)

## **10.3 Visit 3: Day 3**

1. Record any Adverse Experiences
2. Record times when patient received unfractionated heparin or had noncompliance to medication
3. Collect aPTT and anti-Xa 2 hours after fourth dose of heparin (~11:00 AM on day 3)
4. Collect aPTT and anti-Xa 6 hours after fourth dose of heparin (~15:00 PM on day 3)
5. Follow-up aPTT
  - a. If  $<$  36.2 seconds, continue current dose of heparin
  - b. If  $\geq$  36.2 seconds, adjust heparin dose and repeat aPTT and anti-Xa per protocol (APPENDIX 1)

## **10.4 Visit 4: Day 6**

1. Record any Adverse Experiences or side effects
2. Record times when patient received unfractionated heparin or had noncompliance to medication
3. Collect CBC, aPTT, and anti-Xa 6 hours after tenth dose of heparin (~15:00 PM on day 6)
4. Follow up aPTT
  - a. If  $<$  36.2 seconds, continue current dose of heparin
  - b. If  $\geq$  36.2 seconds, adjust heparin dose and repeat aPTT and anti-Xa per protocol (APPENDIX 1)

## **10.5 Weekly Visits (Day 13, 20, 27, 34+ until delivery or discharge from hospital)**

1. Record any Adverse Experiences or side effects
2. Record times when patient received unfractionated heparin or had noncompliance to medication
3. Collect CBC, aPTT, and anti-Xa 6 hours after AM dose of heparin (~15:00 PM)

4. Follow up aPTT
  - a. If  $< 36.2$  seconds, continue current dose of heparin
  - b. If  $\geq 36.2$  seconds, hold or decrease heparin dose and repeat aPTT and anti-Xa per protocol (APPENDIX 1)

### **10.6 Early Withdrawal Visit**

1. Record any Adverse Experiences or side effects
2. Record times when patient received unfractionated heparin or had noncompliance to medication
3. Collect aPTT and anti-Xa 6 hours after AM dose of heparin

## **11 STATISTICAL METHODS AND CONSIDERATIONS**

Prior to the analysis of the final study data, a detailed Statistical Analysis Plan (SAP) will be written describing all analyses that will be performed. The SAP will contain any modifications to the analysis plan described below.

### **11.1 Data Sets Analyzed**

All patients randomized into the study that received two doses of unfractionated heparin and had at least one aPTT measurement available for review will be included within the analysis.

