## **5 CRITERIA FOR EVALUATION**

### **5.1 Primary Efficacy Endpoint**

- Elevated serum aPTT value above the normal range ( $> 36.2$  seconds). Prophylactic dosing of anticoagulation should not cause elevations in coagulation parameters.
  - o To be assessed after 2nd dose, 4th dose, and then weekly while receiving unfractionated heparin
  - o Surrogate marker for whether or not the patient would be eligible for neuraxial anesthesia based on guidelines for neuraxial anesthesia in pregnant women receiving VTE prophylaxis

- American Society for Regional Anesthesia (ASRA)
  - 5,000 units every 12 hours – normal aPTT value or 4 hours since last dose
  - 7,500 – 10,000 units every 12 hours – normal aPTT value and 12 ours since last dose
- Society of Obstetric Anesthesia and Perinatology
  - 5,000 units every 12 hours – always eligible for neuraxial anesthesia
  - 7,500 – 10,000 units every 12 hours – normal aPTT value or 12 hours since last dose

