### **11.4 Analysis of Secondary Endpoints**

Comparison of maternal demographics, baseline characteristics, additional maternal outcomes, and neonatal outcomes between the two groups will be analyzed using Student's t-test for parametric data, Wilcoxon signed-rank test for nonparametric data, and Chi-squared or Fisher's exact test for comparison of proportions. Descriptive statistics will be performed to summarize which dose resulted in a normal aPTT value and anti-Xa within goal range. Multivariate logistic regression analysis will be performed to determine which factors were associated with an elevated aPTT value. Statistical significance will be set at a p-value of  $< 0.05$  or 95% confidence interval not overlapping.

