### **11.5 Sample Size and Randomization**

Based on an informal/pilot review of antepartum admissions at our institution receiving gestational age-based dosing of unfractionated heparin, 40% of patients and an elevated aPTT

value. Assuming 40% of patients receiving gestational age-based dosing and 3% receiving standard dosing had elevated serum aPTT values, a sample size of 18 women in each dosing group would have 80% power (alpha = 0.05) to demonstrate a significant difference in our primary outcome of evaluating the proportion of women with elevated aPTT values after heparin administration. We increased the sample size by 25% to account for post-randomization drop-out or lab sampling errors. We plan to recruit 46 patients.

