Title of Study: Heparin Prophylaxis Dosing for Antepartum Hospitalizations (HEPDOSE)

NCT Number: NCT04635839

Document Date: June 27, 2022

Document: Statistical Analysis Plan

Traditional univariate analysis was performed for our primary and secondary outcomes with Chi-square or Fisher exact test for categorical variable and t-test or Wilcoxon rank-sum test for continuous variables. A logistic regression analysis was performed to further assess the association of elevated aPTT with gestational age-based dosing of unfractionated heparin relative to standard dosing. We also performed a multivariate logistic regression to adjust for confounders. Confounders included in the model were a priori covariates that potentially could affect the response to unfractionated heparin along with baseline characteristics from our univariate analyses comparing study arm groups that had a p value < 0.2. Via a stepwise regression, none of the variable demonstrated a significant effect on our primary outcome. However, for our final model we elected to adjust for creatinine and obesity based on clinical relevance and a priori knowledge of these factors being potential confounders that may not have been detected in our study cohort due to the small sample size.

Statistical significance was defined as a p-value of < 0.05 or non-overlapping 95% confidence intervals (CI). All analyses were conducted using Statistical Analysis Software (SAS), version 9.4 (Copyright 2013, SAS Institute, Inc. Cary, NC).

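### The only analysis set requires two heparin doses and an aPTT, so a few randomised women could be left out of anaesthesia, delivery and neonatal comparisons that need neither (minor)

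*Protocol*

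**What the plan says.** - **Analysis set.** Protocol section 11.1 admits to the analysis "All patients randomized into the study that received two doses of unfractionated heparin and had at least one aPTT measurement available for review". No other set is defined. Both conditions are met or failed after randomisation, unless the baseline aPTT is allowed to count.
- **Secondary endpoints.** Section 11.4 says that "additional maternal outcomes, and neonatal outcomes between the two groups will be analyzed" and lists the tests, but names no population.
- **SAP.** Protocol section 11 promises that "The SAP will contain any modifications to the analysis plan described below". The SAP opens with "Traditional univariate analysis was performed for our primary and secondary outcomes" and does not state a population, so it does not modify section 11.1.
- **Endpoints.** Section 5.2 lists neuraxial nonreceipt or delay, general anaesthesia and delivery delay (each attributed to heparin), then mode of delivery, blood loss, transfusion and neonatal outcomes. For neuraxial and delivery delay, having been given heparin is enough to qualify; an elevated aPTT is not required.
- **Objective.** Section 3.1 names the effect on neuraxial anaesthesia and pregnancy outcomes as part of the primary objective, although the tested primary endpoint is the elevated aPTT.
- **Allowance for loss.** Section 11.5: "We increased the sample size by 25% to account for post-randomization drop-out or lab sampling errors".

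**The concern.** An aPTT endpoint cannot be judged without an aPTT taken after dosing, so the section 11.1 set is reasonable for that endpoint and for anti-Xa. The anaesthesia, delivery and neonatal endpoints are different. A woman who received one dose, or who has no usable aPTT, can still have a fully known delivery.

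Under the plan as written she is removed from those comparisons for something that happened after randomisation in an open-label trial. The comparison is then no longer between the groups as randomised. At stake are the secondary estimates that speak most directly to the clinical part of the stated objective. The trial was not sized for these endpoints, so they will be read as estimates, in arms where one woman carries visible weight.

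**Working it through.** **1. The plan's own numbers.** Section 11.5 assumes 40% against 3%, 80% power and alpha 0.05, and gives 18 per arm. Two-sided alpha is assumed here, with pooled variance and no continuity correction:

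n = [1.96 × √(2 × 0.215 × 0.785) + 0.8416 × √(0.40 × 0.60 + 0.03 × 0.97)]² / 0.37² = (1.139 + 0.437)² / 0.1369 ≈ 18.1, which rounds up to 19.

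Power at 18 per arm is 79.7%, so the stated figure is reproduced to within one woman per arm. Adding 25% gives 18 × 1.25 = 22.5, hence 23 per arm and 46 in total. None of this is in dispute.

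**2. When a woman can fail the two-dose condition.** Inputs are sections 10.1 to 10.3.
- Dose 1: 21:00 on Day 1.
- Dose 2: the Day 2 sample is at about 15:00, 6 hours after dose 2, so dose 2 is at about 09:00 on Day 2.
- Check: the Day 3 sample at about 11:00 is 2 hours after dose 4, so dose 4 is at 09:00 on Day 3. This agrees with 12-hourly dosing.
- Dose 1 to dose 2: 12 hours. Dose 1 to the first scheduled post-dose aPTT: 18 hours.

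A woman who delivers, withdraws or is discharged in those 12 hours is outside the set, yet she has had heparin and can already have a heparin-related neuraxial or delivery delay. The pilot in section 1.1 includes a caesarean delayed because of the timing of a dose alone.

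The exclusion in section 6.3 for delivery expected within 12 hours narrows this window without closing it. For a woman assessed at noon (an assumed time), that horizon ends at midnight, 9 hours before dose 2.

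**3. When a woman can fail the aPTT condition.** This route is narrower.
- One result suffices. Sections 10.2 to 10.4 schedule four post-dose aPTTs by Day 6 (one on Day 2, two on Day 3, one on Day 6), and section 10.5 adds weekly ones. A woman is lost only if every post-dose sample fails, or if she leaves after a failed one.
- Section 10.6 schedules an aPTT at early withdrawal, 6 hours after a morning dose. The first morning dose is dose 2, so this can rescue a woman who leaves after dose 2 but not before it.
- Under the institutional practice in section 1.1, a normal aPTT is needed before neuraxial anaesthesia at 7,500 to 10,000 units. Arm 2 women who need a block after dose 2 are therefore likely to have a clinical aPTT.
- Read literally, the Visit 1 baseline aPTT already meets section 11.1, and then this condition removes almost nobody. Section 11.5, which speaks of "the proportion of women with elevated aPTT values after heparin administration", and section 5.1, where measurement follows dosing "and then weekly while receiving unfractionated heparin", show that a post-dose value is meant.

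**4. Size.** The documents give no expected number of exclusions. The only planning figure is 46 − 2 × 18 = 10 women (5 per arm; 10/46 = 21.7%) for all causes of loss. It is an upper planning figure, because women who leave after two doses and an aPTT stay in the set.

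One woman is 1/23 = 4.3% of an arm. With r events in 23 (r is an assumption), dropping one woman changes the arm's rate as follows:

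| r | all 23 | drop one with the event, (r − 1)/22 | drop one without it, r/22 |
|---|---|---|---|
| 1 | 4.3% | 0.0% (−4.3 points) | 4.5% (+0.2) |
| 3 | 13.0% | 9.1% (−4.0) | 13.6% (+0.6) |

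**5. Direction.** Under the institutional practice, 5,000 units puts no limit on neuraxial anaesthesia. Events between doses 1 and 2 would then arise mainly in second- and third-trimester arm 2 women, and losing them would understate the difference. However, the regional anaesthesia society rule in section 5.1 also restricts 5,000 units ("normal aPTT value or 4 hours since last dose"), so arm 1 events are possible. Dropping women without an event, including any who were never dosed, raises that arm's rate instead. The sign cannot be fixed from the documents.

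**The case against.** The strongest reply is that hardly anyone is affected. Women at risk of delivery within 12 hours are ineligible, admissions are of at least 72 hours, one aPTT is enough, samples are repeated and a withdrawal sample is scheduled. Most of this stands. It reduces the missing-aPTT route to a minor one and leaves the interval between doses 1 and 2 as the clear gap. It does not change the rule as written, and if few women are affected, keeping them costs little.

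It can also be said that section 11.1 was meant only for the aPTT endpoint. That may be so, but the text does not say it, and the SAP does not correct it.

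A third reply also stands: participation ends at delivery or discharge (section 4.1), so women discharged undelivered may lack delivery and neonatal outcomes under any analysis set. That loss could exceed the one described here.

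Three stronger readings are tempting and are not supported:
- A reader might infer that the set systematically hides harm in the gestational-age arm. The direction is uncertain (step 5).
- A reader might infer that the 25% allowance forecasts exclusions under section 11.1. It covers all losses, many of which leave a woman in the set.
- A reader might take the pilot's two affected women in 30 as one event rate. One had no epidural and one had a delayed caesarean, and section 5.2 lists these as separate endpoints. Pooling them to illustrate a bias overstates it.

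**Conclusion.** The point holds at minor severity. The plan's single analysis set applies dose and laboratory conditions to clinical and neonatal endpoints that need neither, and neither section 11.4 nor the SAP provides an alternative.

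The number of women affected is unknown and probably very small. That judgement rests on the imminent-delivery exclusion and on reading the 72-hour criterion as an expected stay; if it means time already spent in hospital, it says less about what follows randomisation. A single excluded woman with an event moves an arm's rate by about 4 points; one without an event moves it by well under 1 point at the event counts assumed above.

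A reader might infer that the primary result is compromised. It is not, because the primary endpoint needs a post-dose aPTT and the sample size allows for loss. Nor is any change in a secondary conclusion shown. The SAP is in the past tense but silent on the population used, so the documents do not show that any woman was in fact excluded.

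**What to change.** - Analyse the anaesthesia, delivery, maternal clinical and neonatal endpoints in all randomised women by assigned arm, wherever outcomes are available.
- Keep the section 11.1 set for the aPTT and anti-Xa endpoints only, and specify at least one post-dose aPTT.
- Report exclusions and missing outcomes by arm and reason.

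The cost is a few sentences in section 11.1 and the SAP, and possibly a re-run of the secondary comparisons if the restricted set was used. There are two downsides. Women with little or no heparin exposure slightly dilute any dose effect. Delivery or neonatal outcomes will still be missing for some women who withdraw consent or go home undelivered; the change does not cure that, which is why those losses should be reported by arm.

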### **11.2 Demographic and Baseline Characteristics**

The following demographic variables will be collected at screening: age, height and weight, body mass index, race, ethnicity. The following baseline characteristics will be collected at screening: gestational age at randomization, gravida, parity, maternal comorbidities.

### **11.3 Analysis of Primary Endpoint**

Analysis of the primary endpoint of whether or not there was an elevation in aPTT in each dosing group will be performed with a Chi-squared test. Comparison will be considered statistically significant at a p-value of  $< 0.05$ .

### **11.4 Analysis of Secondary Endpoints**

Comparison of maternal demographics, baseline characteristics, additional maternal outcomes, and neonatal outcomes between the two groups will be analyzed using Student's t-test for parametric data, Wilcoxon signed-rank test for nonparametric data, and Chi-squared or Fisher's exact test for comparison of proportions. Descriptive statistics will be performed to summarize which dose resulted in a normal aPTT value and anti-Xa within goal range. Multivariate logistic regression analysis will be performed to determine which factors were associated with an elevated aPTT value. Statistical significance will be set at a p-value of  $< 0.05$  or 95% confidence interval not overlapping.

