## 2 STUDY RATIONALE

VTE is one of the leading causes of maternal morbidity and mortality. In efforts to decrease rates of VTE, there is an increased emphasis on administering pharmacologic thromboprophylaxis for antepartum patients with prolonged hospitalizations. Due to physiological changes of pregnancy that may alter the metabolism of unfractionated heparin, it is suspected that dosing of pharmacologic thromboprophylaxis may need to be altered. ACOG's current recommendation is to consider gestational age-based dosing of unfractionated heparin for hospitalized pregnant patients rather than standard dosing. However, there are no prior studies assessing the potential effects of higher dosing. Potential effects of higher dosing include limited receipt of neuraxial anesthesia, increased administration of general anesthesia, delayed time to delivery, and increased bleeding risk. We propose this study to provide a direct comparison of gestational age-based unfractionated heparin dosing to standard dosing of unfractionated heparin for pharmacologic thromboprophylaxis of hospitalized antepartum patients.

For our primary objective, we hypothesize that compared to standard dosing, gestational age-based dosing for VTE prophylaxis is associated with higher rates of elevated aPTT values, a surrogate marker of ineligibility for neuraxial anesthesia. For our additional exploratory objectives, we hypothesize that there will be no significant difference in achieving goal anti-Xa levels (0.2-0.5 IU/mL) between standard dosing and gestational age-based dosing and that particular characteristics (e.g., increased eGFR and higher BMI) are associated with elevated aPTT values with unfractionated heparin administration.

ACOG Practice Bulletin No.123. Thromboembolism in Pregnancy. *Obstet Gynecol* 2011;118:718-729.

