### **3 STUDY OBJECTIVES**

#### **3.1 Primary Objective**

The primary objective is to compare gestational age-based dosing to standard dosing of unfractionated heparin for thromboprophylaxis of pregnant patients with prolonged hospitalizations and determine its effect on receipt of neuraxial anesthesia and pregnancy outcomes.

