## 5.2 Secondary Efficacy Endpoints

- Diagnosis of venous thromboembolism (pulmonary embolism and/or deep venous thromboembolism)
- Nonreceipt or delay of neuraxial anesthesia due to unfractionated heparin defined as inability to receive neuraxial anesthesia due to an elevated aPTT value or because the subject received heparin
- Receipt of general anesthesia due to unfractionated heparin
- Delay in timing of delivery due to unfractionated heparin defined as presence of an indication to proceed with delivery via cesarean delivery or induction of labor but this does not immediately occur due to an elevated aPTT value or because the subject received heparin
- Mode of delivery
- Estimated blood loss at time of delivery
- Receipt of blood transfusion
- CBC for hemoglobin and platelet count (to be assessed weekly while receiving unfractionated heparin)
- Anti-Xa levels (to be assessed with aPTTs while receiving unfractionated heparin)
- Goal anti-Xa level achieved (0.2-0.5 IU/mL)
- Number of times adjustment in dose made
- Development of side effects from heparin administration (e.g bruising, epistaxis)
- Neonatal outcomes
  - Gestational age at delivery
  - Birthweight
  - 1 minute and 5 minute APGAR scores
  - Cord blood gas values: umbilical artery pH, umbilical artery CO2, umbilical artery base excess
  - NICU admission
  - Neonatal death

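### About 22 unranked secondary variables can each be called statistically significant at unadjusted p<0.05, the same label as the primary result, and almost none is marked exploratory

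*Protocol*

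**What the plan says.** Protocol 11.3 names one primary comparison, elevated aPTT by arm, with a chi-squared test at 0.05. Section 11.4 then covers the rest: "Comparison of maternal demographics, baseline characteristics, additional maternal outcomes, and neonatal outcomes between the two groups will be analyzed using" t-tests, Wilcoxon tests, and chi-squared or Fisher tests. It closes with one rule for all of them: "Statistical significance will be set at a p-value of" below 0.05, or 95% intervals that do not overlap. The synopsis statistics row repeats this.

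The SAP does the same. "Traditional univariate analysis was performed for our primary and secondary outcomes", and "Statistical significance was defined as a p-value of < 0.05 or non-overlapping 95% confidence intervals (CI").

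Section 5.2 lists the secondary efficacy endpoints without ranking, from VTE and "Receipt of general anesthesia due to unfractionated heparin" through to neonatal death. Neither document gives a testing order, an alpha split, a gate on the primary result, or a statement that secondary p-values are supportive only.

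The word exploratory occurs once, in section 2: "For our additional exploratory objectives, we hypothesize that there will be no significant difference in achieving goal anti-Xa levels". In that sentence it covers goal anti-Xa and the characteristics associated with elevated aPTT, and nothing else.

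Section 3.1 says that the primary objective is to compare the two dosing schemes and "determine its effect on receipt of neuraxial anesthesia and pregnancy outcomes".

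**The concern.** A result on cord-gas pH, birthweight or delivery delay with p=0.04 would carry the same label as the aPTT result, although the trial is sized only for aPTT. With this many comparisons in 46 women, one such result can easily arise by chance.

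Section 3.1 makes this more than a matter of presentation. Neuraxial receipt and pregnancy outcomes are part of the primary objective, but they are measured directly only by secondary endpoints. A chance finding there could be reported as an answer to the trial's main question.

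The same sentence in 11.4 also tests baseline characteristics. Under sound randomization, any baseline difference that reaches p<0.05 is chance. The SAP nevertheless uses baseline p<0.2 to screen covariates.

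**Working it through.** **The plan's own figure.** Section 11.5 assumes 40% against 3%, 80% power and alpha 0.05, and gives 18 per arm. With the two-sided pooled normal formula, the mean proportion is 0.215 and

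n = [1.96·√(2·0.215·0.785) + 0.8416·√(0.40·0.60 + 0.03·0.97)]² / 0.37² = 18.1, rounded up to 19.

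Power at 18 per arm is 79.7%, so the stated figure is reproduced to within one woman per arm. Inflation gives 18 × 1.25 = 22.5, hence 23 per arm and 46 in total. The documents state no family-wise error rate for the secondary endpoints, so there is no figure of that kind to reproduce.

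**Count of secondary variables (5.2).**
- There are 12 maternal items, or 13 variables with hemoglobin and platelets separated.
- There are 6 neonatal items, or 9 variables with two Apgar scores and three cord-gas values separated.
- The total is 13 + 9 = 22 variables (18 listed items). If goal anti-Xa is only described, as 11.4 may intend, 21 remain.

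**Upper bound.** If all are null, independent and tested at an exact 0.05 (two-sided assumed, since sidedness is not stated):
- 22 tests: 1 − 0.95²² = 67.6%, with 22 × 0.05 = 1.1 false positives expected
- 21 tests: 1 − 0.95²¹ = 65.9%
- 18 tests: 1 − 0.95¹⁸ = 60.3%

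**Allowing for rare events.** With 23 per arm, Fisher's test at a true rate of 2% rejects about 0.01% of the time, and at 5% about 0.3%. VTE (below 2% by section 2.1) therefore contributes almost nothing.

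A simulation under no arm effect used 12 continuous endpoints (t-test) and 10 binary ones (chi-squared, or Fisher when an expected count is below 5). The binary rates are assumed:
- VTE and neonatal death 1%
- general anesthesia 2%
- delivery delay 5%
- neuraxial problem and transfusion 7%
- side effects 20%
- goal anti-Xa 30%
- mode of delivery and NICU admission 50%

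**Allowing for real effects.** Six endpoints may truly differ. Anti-Xa level, goal anti-Xa and number of dose adjustments follow from dose. Neuraxial problems, heparin-related general anesthesia and heparin-related delivery delay follow from the institution's neuraxial rule, which depends on dose (section 1.1). That leaves 22 − 6 = 16. Removing VTE and neonatal death as effectively untestable leaves 14.

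Chance of at least one false positive, by assumed common correlation:

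| Null endpoints | 0 | 0.3 | 0.5 | 0.7 | 0.8 |
|---|---|---|---|---|---|
| 22, all at full 5% size | 68% | 57% | 44% | 30% | 23% |
| 22, rare events allowed for | 57% | 50% | 42% | 32% | 26% |
| 19 (three anti-Xa and dose items removed), rare events allowed for | 50% | 44% | 37% | 29% | not run |
| 14, full size | 51% | 44% | 35% | not run | 20% |
| 8, full size | 34% | 30% | 25% | not run | 16% |

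The second row carries about 0.8 expected false positives at every correlation from 0 to 0.7. The 0.8 entry in that row comes from a separate run of the same design.

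**The interval criterion.** With equal standard errors, two 95% intervals fail to overlap only when |z| exceeds 2 × 1.96/√2 = 2.77, which is p of about 0.006. This is stricter than p<0.05, so offering it as an alternative adds no further inflation.

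**The case against.** The strongest reply is that one primary endpoint has its own test and sample size, and that the others are openly called secondary. Unadjusted secondary p-values in a 46-woman single-center trial are then largely a matter of interpretation. The first part stands: the secondary tests do not affect the primary error rate. The second does not fully answer the point. The plan states a significance rule for these endpoints, and it applies the exploratory label to some items and not to others.

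Four stronger readings are tempting and should not be drawn.

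- **A false-positive claim is more likely than not.** That needs at least 14 independent null tests at full size (13 give 48.7%, 14 give 51.2%). With moderate correlation the figures fall below one half.
- **A stated 5% family-wise rate is exceeded several-fold.** The documents give 0.05 as the level of a single comparison and promise nothing for the family.
- **The primary objective rests wholly on the secondary endpoints.** Sections 2 and 5.1 present elevated aPTT as a surrogate for ineligibility for neuraxial anesthesia, so the primary test addresses part of that objective. The pregnancy outcomes have no such link.
- **All 22 endpoints are null.** Several are tied to dose or to the neuraxial rule, and section 2 also anticipates more bleeding at higher doses. A difference there need not be chance.

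Baseline testing is a separate matter and adds nothing to the count of 22. It belongs in the same correction only because the same sentence in 11.4 governs it.

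**Conclusion.** The concern holds as a substantial and uncontrolled risk. About 22 secondary variables can be declared significant at unadjusted p<0.05 with no hierarchy, and only one of them, goal anti-Xa, falls under an exploratory label.

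The family-wise false-positive risk is at most about 68%. It is plausibly about 30-57% for correlations from 0 to 0.7 with rare events allowed for, and about 20-51% if only about 14 endpoints are null and testable. Even with 8 null endpoints it is 16-34%, at least three times the 5% attached to a single test. All correlations, and all event rates except the below-2% VTE figure, are assumptions, so the ranges matter more than any single value.

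The aPTT comparison is sound on this point. What needs protecting is the meaning of any secondary result that could be read as answering section 3.1. This is an inexpensive improvement and not a flaw in the primary analysis.

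**What to change.** In 11.4, the synopsis statistics row and the SAP:

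- Limit the claim of statistical significance to the single aPTT test in 11.3.
- State that the secondary endpoints in 5.2 are exploratory and unadjusted. Report them as between-arm differences with 95% confidence intervals, and call any p-values nominal.
- Report baseline characteristics descriptively, without tests, and remove the SAP's baseline p<0.2 covariate screen that depends on those tests. The SAP says that its final model adjusts for creatinine and obesity on clinical grounds, so that model does not need the screen.

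Do not add a gated key secondary endpoint now unless it is disclosed as post hoc. The SAP is written in the past tense and already describes model results, so a gate introduced at this stage could not be presented as prespecified. The exploratory labelling can still be applied in reporting.

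The cost is wording only, with no extra patients or data. The downside is that an isolated secondary p<0.05 can no longer be called significant.

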### **10.1 Visit 1: Day 1**

1. Review the study with the subject (subject's legal representative) and obtain written informed consent and HIPAA authorization and assent, if appropriate.
2. Assign the subject a unique screening number.
3. Record demographics data.
4. Record medical and surgical history
5. Record concomitant medications.
6. Collect blood for clinical laboratory tests (CBC, aPTT, anti-Xa, serum creatinine).
7. Randomize subject
8. Order unfractionated heparin dosing that subject is randomized to (first dose ordered for 21:00 PM the day patient is randomized)

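### Hemoglobin and platelet count have a pre-heparin baseline, but the plan writes in no use of it and does not name the on-treatment value compared, which gives up precision

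*Protocol*

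**What the plan says.** Protocol 5.2 lists among the secondary endpoints "CBC for hemoglobin and platelet count (to be assessed weekly while receiving unfractionated heparin".

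The baseline is in Protocol 10.1. Step 6 of Visit 1 reads "Collect blood for clinical laboratory tests (CBC, aPTT, anti-Xa, serum creatinine", randomization is step 7, and step 8 orders heparin with the "first dose ordered for 21:00 PM the day patient is randomized". Appendix 2 schedules the same Visit 1 count in both arms. The baseline count therefore precedes both allocation and treatment.

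The first on-treatment count comes at Visit 4, in Protocol 10.4: "Collect CBC, aPTT, and anti-Xa 6 hours after tenth dose of heparin". Further counts follow weekly until delivery or discharge (10.5). The early withdrawal visit (10.6) collects aPTT and anti-Xa but no blood count.

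On analysis, Protocol 11.4 says "Comparison of maternal demographics, baseline characteristics, additional maternal outcomes, and neonatal outcomes between the two groups will be analyzed using Student's t-test" or a Wilcoxon test. The SAP says "Traditional univariate analysis was performed for our primary and secondary outcomes", with "t-test or Wilcoxon rank-sum test for continuous variables". The only covariate-adjusted model in either document is the logistic regression for elevated aPTT, where the SAP says "for our final model we elected to adjust for creatinine and obesity". Protocol 11.2 does not list the blood count among the baseline characteristics. Neither document mentions change from baseline, a baseline covariate or a repeated-measures model for hemoglobin or platelets.

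**The concern.** A woman's own pre-treatment hemoglobin or platelet count is likely to be a strong predictor of her value a few days later. A comparison that does not use it carries the full between-woman spread into the standard error. The trial plans 46 women, a number set by the aPTT contrast and not by these endpoints, so there is little precision to spare.

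The endpoints do bear on the trial's question. Protocol section 2 names increased bleeding risk as a possible effect of the higher dosing, and section 2.1 names thrombocytopenia as a rare side effect. With a wider interval than necessary, a real shift in either count is more likely to go undetected.

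The analysed quantity is also left open. With counts on Day 6 and weekly after that, a reader cannot tell which value, or what summary of several, enters the test.

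**Working it through.** **The plan's own figure.** There is no sample-size calculation for these endpoints. The only one is for aPTT (Protocol 11.5): 40% versus 3%, 80% power, alpha 0.05, 18 per arm. With the pooled formula, two-sided, n = [1.96 × √(2 × 0.215 × 0.785) + 0.842 × √(0.40 × 0.60 + 0.03 × 0.97)]² / 0.37² = 18.1, rounded up to 19. Power at 18 per arm is 79.7%. The stated figure reproduces to within rounding and is not in dispute. The inflation is 18 × 1.25 = 22.5, rounded up to 23 per arm, or 46 in all.

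**Inputs for this point.** From the documents: at most 23 women per arm, 1:1 allocation and 5% significance, taken as two-sided. Assumed, because the documents give none: the baseline-to-follow-up correlation rho (0.3 to 0.8), and for illustration a hemoglobin difference of 0.75 g/dL with SD 1.2, so d = 0.75/1.2 = 0.625.

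**Formulas.**
- Residual variance after adjustment, relative to the unadjusted test: 1 − rho².
- Women an unadjusted test would need to match 46 adjusted: 46/(1 − rho²).
- Power: noncentral t with noncentrality d × √(n/2) / √(1 − rho²), on 44 degrees of freedom unadjusted and 43 adjusted at n = 23 per arm. The stricter version multiplies the adjusted variance by 1 + 1/(N − 4), which is 1 + 1/42 at N = 46.

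**Results.** The last column uses 12 per arm, an assumed figure to show what fewer contributing women would do.

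| rho | Variance cut | Equivalent N | Power, 23 per arm | Same, small-sample factor | Power, 12 per arm, with factor |
|---|---|---|---|---|---|
| unadjusted | – | 46 | 54.5% | – | 31% |
| 0.3 | 9% | 51 | 58.4% | 57.4% | 32% |
| 0.5 | 25% | 61 | 66.7% | 65.7% | 38% |
| 0.7 | 49% | 90 | 82.7% | 81.8% | 51% |
| 0.8 | 64% | 128 | 93.2% | 92.7% | 66% |

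If rho were zero, the factor would lower power at 23 per arm from 54.5% to 53.5%, so a useless baseline costs about one point. For a much smaller assumed effect of 0.25 SD, power at 23 per arm moves only from 13% to 14%, 16%, 21% and 28%.

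In terms that need no assumed effect, the difference detectable with 80% power at 23 per arm falls from 0.85 SD to 0.82, 0.74, 0.61 and 0.51 SD. At 18 per arm it falls from 0.96 SD to 0.93, 0.85, 0.70 and 0.59 SD.

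**Who contributes.** The Day 6 draw at about 15:00 falls 5 × 24 − 6 = 114 hours after a first dose at 21:00 on Day 1. Inclusion asks for an antepartum admission of at least 72 hours, and the analysis set (11.1) needs only two doses and one aPTT. A woman can satisfy both and leave before any on-treatment count is scheduled. The 23-per-arm column is therefore an upper bound for its assumed effect, SD and rho.

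**Change scores.** A t-test on change from Visit 1 has relative variance 2(1 − rho), which is below 1 only when rho exceeds 0.5. Covariance adjustment has relative variance 1 − rho², which is never larger than either alternative, apart from the small-sample factor.

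**The case against.** The strongest reply is that a reader might infer the plan has chosen to ignore the baseline draw, and the documents do not say that. Section 11.4 and the SAP do not name hemoglobin or platelets, which fall under the general wording for maternal and continuous outcomes. A t-test on change from Visit 1 would fit that wording. This stands: what can be shown is that no use of baseline is written in and that the analysed value is undefined. Protocol 11.4 does name a Wilcoxon signed-rank test, which is paired. It is named for comparing the two groups, however, and the SAP names the two-sample rank-sum test, so it is not evidence of a baseline-adjusted analysis.

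A reader might also infer that the unadjusted test is biased, or that a chance baseline difference would invalidate it. That does not follow. Allocation is randomized 1:1, and chance imbalance is already covered by the 5% level. Restriction to women still in hospital at the time of the count is a separate limitation. It affects adjusted and unadjusted analyses alike, and adjusting for baseline does not by itself remove it.

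The power figures rest on assumed values and on more women than will contribute. This stands too. At rho 0.3 the gain is only 3 to 4 points, and for small effects the comparison stays uninformative under either method.

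Finally, the consequence is limited. No stated hypothesis and no stopping rule depends on these counts, and a rare thrombocytopenia is a matter of individual falls more than of a shift in means. That bears on priority, not on whether the adjustment is worth having.

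**Conclusion.** The point holds as a minor improvement to a secondary analysis. The plan schedules a pre-heparin hemoglobin and platelet count for every woman, specifies only unadjusted two-sample tests, and leaves the compared on-treatment value unnamed.

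The cost is precision only, and the primary endpoint is unaffected. The relative variance reduction is rho squared whatever the effect or SD. Its actual size cannot be fixed from the documents because they give no rho. A correlation well above zero between counts about five days apart is plausible but remains an assumption. The downside if rho is near zero is about one point of power.

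**What to change.** In Protocol 11.4 and the SAP, name hemoglobin and platelet count explicitly and specify one of two analyses:
- analysis of covariance of one pre-named on-treatment value (for example Day 6) on arm and the woman's own Visit 1 value; or
- a mixed model over the Day 6 and weekly values, with arm, time and the Visit 1 value as covariate.

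Report the adjusted difference with its 95% confidence interval and the number of women contributing in each arm. State that the comparison is limited to women with an on-treatment count.

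The cost is a few lines of text and one residual degree of freedom in the covariance analysis, with no new data. The SAP is written in the past tense and already reports modelling results. If these endpoints have been analysed, the adjusted estimate should be added beside the unadjusted one and labelled post hoc.
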